11.3.4.1 Serious Adverse Events

All AEs will be assessed as either serious or non-serious. An SAE or serious adverse reaction is defined as any untoward medical occurrence that at any dose:

• Results in death

- Is immediately life-threatening, (the term "life-threatening" in the definition of "serious" refers to an event in which the subject is at risk of death at the time of the event; it does not refer to an event which hypothetically might have caused death if it were more severe)
- Requires in subject hospitalization or prolongation of existing hospitalization (hospitalization for elective surgery for a baseline condition is not considered an AE)
- Results in persistent or significant disability/incapacity (permanent or substantial disruption of a person's ability to conduct normal life functions)
- Is a congenital anomaly/birth defect
- Is a medically important event that may not be immediately life-threatening or result in death or hospitalization, but may jeopardize the subject and may require medical or surgical intervention to prevent one of the above listed outcomes

Important medical events that may not have resulted in death, be life-threatening, or require hospitalization may be considered an SAE when, based upon appropriate medical judgment, they may jeopardize the subject and may require medical or surgical intervention to prevent one of the outcomes listed in this definition. Examples of such medical events include allergic bronchospasm requiring intensive treatment in an emergency room or at home, blood dyscrasias, or convulsions that do not result in inpatient hospitalization, or the development of drug dependency or drug abuse.

Hospitalization is a criterion for assessment of seriousness. To qualify as serious under the criteria of "hospitalization," a hospital admission of at least a 24-hour period is required. If a subject is retained the emergency room greater than 24 hours, but not admitted for medical care, these cases should be evaluated individually, as criteria such as "medically significant" may also apply.

Hospitalization without a medical AE should not be considered either serious or an AE. Examples include the following:

- Admission for treatment of a pre-existing condition not associated with the development of a new AE or with worsening of the pre-existing condition (e.g., for work-up of persistent pretreatment lab abnormality)
- Hospitalization for a purpose unrelated to the study (e.g.,, "planned" or elective surgery scheduled prior to study participation) would not ordinarily need to be reported, unless a complication occurred which otherwise caused prolongation of this hospitalization

- Protocol-specified admission or procedure (e.g., cataract surgery required by a study protocol; or overnight stay for monitoring due to protocol required surgery, with no associated SAE or complication necessitating prolonged stay)
- Social admission (e.g., social hospitalization for purposes of respite care)

Note: A spontaneous abortion and elective abortion will be considered as SAEs, and must be reported to the sponsor within 24 hours of your awareness of the event.

11.3.4.2 Assessment of Severity and Causality of Adverse Events

The severity assigned to an AE should be determined by the maximum severity of the AE. The categories described below should be used to estimate the severity of AEs:

- Mild: Awareness of a sign or symptom but is easily tolerated, requires no treatment and does not interfere with subject's daily activities.
- Moderate: Low level of concern to the subject and may interfere with daily activities, but can be relieved by simple therapeutic care.
- Severe: Interrupts the subject's daily activity and requires systemic therapy or other treatment.

The investigator should assess the relationship of the AE, if any, to the study drug as either "Related" or "Not Related."

- **Related:** There is at least a reasonable possibility that the AE/SAE is related to the study drug. Reasonable possibility means that there is evidence to suggest a causal relationship between the drug and the AE.
- **Not Related:** There is little or no reasonable possibility that the AE/SAE is related to the study drug. This assessment implies that the AE/SAE has little or no temporal relationship to the study drug and/or a more likely or certain alternative etiology exists.

The following should be taken into account when assessing AE/SAE causality:

- Positive temporal relationship to study drug, such as if the study drug was withdrawn and the SAE resolved or the event recurred after re introduction
- If there is a reasonable possibility that the AE is associated with an underlying or concomitant illness
- Possible association with previous or concomitant therapy

- No temporal relationship to the study drug and/or a more likely alternative etiology exists
- If the AE is directly related to study procedures or there is a lack of efficacy

11.3.4.3 Procedures for Reporting Adverse Events and Serious Adverse Events

Throughout the course of the study, efforts will be made by the investigator to remain alert to possible AEs that are either systemic or ocular in nature. The period of observation for collection of AEs extends from the time the subject and parent/legal guardian gives informed consent/assent until the last study visit or discontinuation from the study. The first concern will be the safety of the subject, and appropriate medical intervention will be made.

The investigator or designee will elicit reports (i.e., via direct questioning, observation, clinical evaluation) of AEs from the subject at each study visit and record all AEs. The investigator will document the dates of onset, progress, outcome, and resolution of such AEs. The investigator will also provide an assessment of all AEs as to the severity, causal relationship to study drug, and causal relationship to study protocol.

It is the investigator's responsibility to document all AEs that occur during the study. The AEs should be documented as a single medical diagnosis. When this is not possible, the AE should be documented in terms of signs and/or symptoms observed by the investigator or reported by the subject and/or their parent/legal guardian at each study visit.

All AEs occurring after the subject and their parent/legal guardian signs the assent/informed consent through the last study visit must be reported, regardless of whether or not the AEs are considered drug-related. All AEs, whether in response to a query, observed by the clinical center personnel, or reported spontaneously by the subject and/or their parent/legal guardian, will be recorded.

At each visit during the study, the subject will be assessed for the occurrence of new and ongoing AEs. Cutaneous tolerability signs and symptoms that result in the subject's requiring a concomitant therapy or discontinuation from the study will be reported as an AE. The following data will be collected on all AEs and recorded on the appropriate eCRF:

- Event name (diagnosis preferred, if unknown, record the signs/symptoms)
- Onset date and end date
- Maximum intensity (severity)
- Seriousness
- Action taken regarding study drug

- Corrective treatment, if given
- Outcome

In addition, the investigator's assessment of causality will be recorded.

Any SAE must be reported to the sponsor, independent of the circumstance or suspected cause, within 24 hours from the time the event was reported to the investigator. All SAEs experienced from the date of consent through at least 30 days after the last dose of study drug must be reported to the sponsor regardless of the relationship to the study drug or the protocol. For events occurring beyond the minimum 30-day period after the last dose of study drug, or for any timeframe afterward deemed medically significant, only SAEs considered related to the study drug should be reported promptly to the sponsor.

Within 24 hours of notification the investigator will fax or email a completed Serious Adverse Event Report to the following:

Investigators should not wait to receive additional information to document the event before notifying the sponsor of an SAE. If only limited information is initially available, follow-up reports are required. If the investigator becomes aware of any new information regarding a SAE (ie, resolution, change in condition, or new treatment), a new SAE Form must be completed and faxed/emailed to the sponsor within 24 hours. The original SAE Form is not to be altered. The report should be marked as a "follow-up report" and describe whether the event has resolved or continues and how the event was treated. Additional relevant information such as hospital records and autopsy reports should be provided to the sponsor as soon as they are available.

Should the investigator become aware of an SAE (regardless of its relationship to investigational product) that occurs within 30 days after stopping the study drug, the SAE must be reported in accordance with procedures specified in this protocol.

The investigator should take all appropriate measures to ensure the safety of the subjects, notably he/she should follow a subject with an SAE until the event has resolved or the condition has stabilized. This may imply that follow-up will continue after the subject has left the study, and that additional investigations may be requested by the sponsor.

11.3.4.4 Submitting an Expedited Safety Report to the Institutional Review Board

Any suspected unexpected serious adverse reaction warrants expedited reporting. In addition, any unexpected SAE related to a subject's participation in the study (or conduct of study), regardless if the study drug was administered, will be evaluated by Global Safety and Vigilance to determine if expedited reporting is required. For example, an unexpected, serious and severe reaction which could be associated to the study procedures, and which could modify the study conduct requires expedited reporting.

Each expedited safety report will routinely include a brief cover memorandum, the completed MedWatch Form FDA 3500A or Council for International Organizations of Medical Sciences I Form, a clinical analysis of the event with any similar events that have occurred with the product, and any additional pertinent information recommended by the study medical monitor. Once the report is compiled, the clinical center investigator must submit the expedited safety report to the local IRB/IEC within the required reporting timeframe. Follow-up reports should be submitted when requested or when pertinent information becomes available. The principal investigator must retain a complete copy of each expedited safety report as it was submitted to the IRB/IEC. It is important that the principal investigator review these expedited reports, as they contain safety information that may be relevant to each of the participating subjects.

11.3.5 Pregnancy

All pre-menses females (9 and older) and female subjects of childbearing potential must use an effective method of birth control during the course of the study, in a manner such that risk of contraceptive failure is minimized. Abstinence is allowed as a birth control method.

Before enrolling a female subject of childbearing potential in this clinical study, the investigator must review the following information about study participation:

- Informed consent/assent requirements.
- Contraceptives in current use.

Following review of this information and appropriate counseling for the subject and their parent/legal guardian, the investigator or designee and the subject and parent/legal guardian must sign the assent/informed consent before study enrollment.

During the study, all pre-menses females (9 and older) and female subjects of childbearing potential should be instructed to contact the investigator immediately if they suspect they might be pregnant (e.g., missed or late menstrual period).

If a subject or investigator suspects that the subject may be pregnant prior to study enrollment, the study drug must be withheld until the results of laboratory pregnancy testing are available. If pregnancy is confirmed, the subject must not receive study drug and must not be enrolled in the study. If pregnancy is suspected while the subject is receiving study treatment, the study drug must immediately be withheld until the result of pregnancy testing is known. If pregnancy is confirmed, the study drug will be permanently discontinued and the subject will be followed until the pregnancy comes to term. A Pregnancy Report form will be submitted to the sponsor, initially within 24 hours of the investigator's awareness and at the end of the pregnancy, which includes the outcome of the pregnancy and any complications occurring during the pregnancy or the delivery. If a pregnancy is associated with an SAE, and SAE report form and the pregnancy report form should be submitted to the sponsor within 24 hours of the investigators awareness.

12 Statistics

All statistical processing will be performed using SAS® unless otherwise stated. No interim analyses are planned. Except where noted, all statistical tests will be two-sided and will be performed at the 0.05 level of significance.

Descriptive statistics will be used to provide an overview of the efficacy and safety results. For categorical parameters, the number and percentage of subjects in each category will be presented. For continuous parameters, descriptive statistics will include n (number of subjects), mean, standard deviation, median, minimum, and maximum. Appropriate inferential statistics will be used for the primary, secondary, and tertiary efficacy variables.

The primary method of handling missing efficacy data will be the method of Markov Chain Monte Carlo (MCMC) multiple imputation. As a sensitivity analysis, the last observation carried forward method (LOCF) will be used (i.e., the last available on-therapy observation for a subject will be used to estimate subsequent missing data points). Additionally, a tipping point analysis will be performed for the primary endpoint. No imputations will be made for missing safety data.

A statistical analysis plan (SAP), describing all statistical analyses will be provided as a separate document. The SAP will be finalized prior to unblinding of the study treatments.

12.1 Subject Disposition

A tabulation of subject disposition will be provided. The tabulation will include the numbers of subjects who enter the study, complete the study, and discontinue the study. The reasons for discontinuation will be included.

12.2 Demographics and Baseline Characteristics

Subject demographic and baseline characteristics will be summarized by treatment group for the intent-to-treat (ITT) population, the Week 6 per protocol (PP) population, and the Week 10 PP population. For continuous variables (e.g., age) comparisons among the 2 treatment groups will be conducted using a 2-way analysis of variance with factors of treatment and analysis center. Ethnicity and race will be analyzed with a Cochran-Mantel-Haenszel (CMH) test stratified by analysis center. Past and current medical conditions, as well as history of disease will not be compared statistically.

12.3 Protocol Deviations

All protocol deviations will be reported to the sponsor and recorded throughout the study. A data listing of protocol deviations will be included in the final study report.

12.4 Compliance

The extent of exposure to study drug in each treatment group will be summarized by total number of days of exposure, total number of applications, number of missed applications, percentage of expected applications applied and number and percentage of subjects who are compliant. A subject will be considered compliant with the dosing regimen if the subject applied 80% to 120% of the expected number of applications while enrolled in the study.

12.5 Efficacy

The primary efficacy endpoint will be the percent of subjects with treatment success, defined as at least a 2-grade improvement from Baseline in IGA score and an IGA score equating to clear or almost clear.

12.5.1 Primary Efficacy

The primary efficacy endpoint will be used to compare twice daily application of IDP-124 Lotion and Vehicle Lotion.

The percentage of subjects with treatment success at Week 6 will be analyzed using CMH test stratified by analysis center.

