7.1 Investigators and Study Administrative Structure

Approximately 20 investigational centers are planned to participate in this study. Each clinical investigator will be required to provide a copy of his/her curriculum vitae and medical license, complete a financial disclosure statement, and generate a list of study personnel who will be involved in the study, with a summary of their roles and qualifications.

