8.1 Subject Inclusion Criteria

Subjects meeting all of the following criteria will be eligible for study entry:

- 1. Male or female at least 2 years of age and older.
- 2. Written and verbal informed consent must be obtained; subjects less than age of consent must sign an assent (as required per IRB/IEC guidelines) for the study and a parent or a legal guardian must sign the informed consent (if subject reaches age of consent during the study they should be re-consented at the next study visit).
- 3. Nonimmunocompromized male or female who failed to respond adequately to other topical prescription treatment for AD or for whom those treatments are not advisable.
- 4. Clear diagnosis of AD fulfilling the diagnostic criteria of Hanifin and Rajka¹³ that affects ≥ 5% of TBSA (see Appendix 17.4 for full list of diagnostic criteria to reference); subject should have had a diagnosis of AD for at least 3 months; i.e., determined by subject-reported or parent-reported duration of subject experiencing itchy and dry skin for 3 months or longer (at Screening and Baseline visits).
- 5. Subject must have a score of 3 (moderate) or 4 (severe) on the IGA scale at the Screening and Baseline visits.
- 6. Subjects must be willing to comply with study instructions and return to the clinic for required visits; subjects under the age of consent must be accompanied by the parent or legal guardian at the time of assent/consent signing.

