11.2.2 Investigators Global Assessment

At Screening, Day 1 (Baseline), Week 1, 2, 4, 6 and 10 study visits (all visits), AD severity will be determined by the investigator/evaluator based on a global assessment of the inflammatory signs of AD. Evaluations will be graded on a static scale ranging from 0 (clear) to 4 (severe) as shown in the following table:

Score	Grade	Description	
0	Clear	No inflammatory signs of AD (no erythema, no induration/papulation, no lichenification, no oozing/crusting). Post-inflammatory hyperpigmentation and/or hypopigmentation may be present.	
1	Almost clear	Barely perceptible erythema, barely perceptible induration/papulation, and/or minimal lichenification. No oozing or crusting.	
2	Mild	Slight but definite erythema (pink), slight but definite induration/papulation, and/or slight but definite lichenification. No oozing or crusting.	
3	Moderate	Clearly perceptible erythema (dull red), clearly perceptible induration/papulation, and/or clearly perceptible lichenification. Oozing and crusting may be present.	
4	Severe	Marked erythema (deep or bright red), marked induration/papulation, and/or marked lichenification. Disease is wide-spread in extent. Oozing or crusting may be present.	

The primary efficacy variable is the IGA score at Week 6. Treatment success is defined as achieving clear to almost clear (i.e., a score of 0 or 1) and at least a 2-grade improvement in the IGA score at the end of treatment compared with Baseline.

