12.5.6 Subgroup Analyses

Subgroup analyses will be conducted for the ITT population for the following subgroups: Baseline IGA, sex, age, ethnicity, race, and geographic region. Subgroup analyses will be conducted on the primary efficacy endpoint and will contain only descriptive statistics.

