12.8.2 Sample Size Determination

The following power calculations were computed using the IGA efficacy results from the Pimecrolimus Lotion, 1% (Elidel) NDA 21-302. Considerations were given the change in expected entry level severity of the current study. Nquery Advisor Version 7.0 with the Fisher's exact test option was used to calculate the power using a 2-sided test with an alpha of 0.05. The following table presents the efficacy estimates used in this power calculation.

Percent Dichotomized IGA Success* for Treatment Groups

	Pimecrolimus Lotion, 1%	Vehicle
Percent	23.6%	6.3%
Success		

* Success was defined as at least a 2-grade improvement from Baseline in the IGA score and an IGA score equating to "Clear" or "Almost Clear".

Overall, 232 IDP-124 Lotion treated subjects and 116 vehicle lotion treated subjects will have greater than 95% power to detect a statistically significant outcome for a 2-sided test with an alpha level of 0.05.

It was noted that the estimates extracted from the above studies are based on the LOCF method of handling missing values while the proposed Phase 3 analysis will account for missing values using multiple imputations. The power stated above sufficiently exceeds 95% which will compensate for the difference in handling of missing data.

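### The primary CMH stratifies by analysis center only; adding baseline IGA as a main effect beside center would bring a small gain in precision at little cost

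*Combined protocol and SAP*

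**What the plan says.** - **Primary test.** Section 12.5.1 says that the Week 6 success percentage "will be analyzed using CMH test stratified by analysis center". The Synopsis repeats this, and Section 12.5.2 uses the same method for secondary endpoints.
- **Entry.** Section 8.1: "Subject must have a score of 3 (moderate) or 4 (severe) on the IGA scale at the Screening and Baseline visits".
- **Endpoint.** Section 11.2.2 defines success as "achieving clear to almost clear (i.e., a score of 0 or 1) and at least a 2-grade improvement in the IGA score".
- **Randomization.** Sections 9.1 and 9.2 describe a 2:1 computer-generated schedule and mention no baseline IGA stratum.
- **Other uses of baseline IGA.** It is in the variable list of the imputation model (Section 12.8.3). It is also one of the purely descriptive subgroups in Section 12.5.6: "Baseline IGA, sex, age, ethnicity, race, and geographic region". The GEE sensitivity model (Section 12.5.5.2) has treatment, center and visit, but not baseline IGA. No inferential analysis of the primary endpoint adjusts for it.
- **Contrast.** The tertiary TBSA analysis (Section 12.5.3) does adjust for its baseline value.
- **Power.** Section 12.8.2 assumes 23.6% vs 6.3% and states that "232 IDP-124 Lotion treated subjects and 116 vehicle lotion treated subjects" "will have greater than 95% power to detect a statistically significant outcome".

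**The concern.** Baseline IGA is part of how the endpoint is scored: the same target is one grade further away for a severe subject. It is therefore likely to predict success, and adjusting a randomized comparison for a strong predictor usually sharpens it. The plan instead spends its stratification on about 20 centers.

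Three things are at stake, all modest:
- power if the effect is weaker than planned;
- protection if one arm happens to receive more severe subjects;
- the IGA-success secondaries, which sit in a fixed sequence that stops at the first non-significant result and for which no power is stated.

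**Working it through.** **1. The plan's own figure.** Inputs from Section 12.8.2: 232 vs 116 subjects, 23.6% vs 6.3%, Fisher's exact test, two-sided alpha 0.05. Full enumeration gives power of 99.3%, and 97.1% if 20% of subjects are lost. This agrees with the stated figure of more than 95%.

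**2. Grades needed.** From 3 to 1 is 2 grades; from 4 to 1 is 3 grades.

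**3. Chance imbalance.** The SD of the arm difference in severe share s is √[s(1−s)(1/232 + 1/116)].
- s = 20%: √(0.16 × 0.01293) = 4.5 points
- s = 30%: √(0.21 × 0.01293) = 5.2 points
- s = 35%: √(0.2275 × 0.01293) = 5.4 points

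To see the effect on the result, take s = 30% and a severe-vs-moderate odds ratio of 0.25 (both assumed), with the overall rates held at plan. Success is then 29.6% moderate and 9.5% severe on active, and 8.1% and 2.1% on vehicle. A one-SD imbalance with more severe subjects on active raises the active severe share by 5.2/3 = 1.7 points and lowers the vehicle share by 3.5 points. The observed difference shrinks by 1.7 × 0.201 + 3.5 × 0.060 ≈ 0.6 points, against a planned 23.6 − 6.3 = 17.3.

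**4. Crossing IGA with center.** With 348/20 = 17.4 subjects per center and 30% severe, a center has about 5.2 severe subjects, or 3.5 active and 1.7 vehicle. In simulation (20,000 trials per scenario, 20 equal centers, no center effect, design rates, 30% severe), mean z was:

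| Odds ratio | CMH by center | CMH by center × IGA | CMH by IGA alone |
|---|---|---|---|
| 0.5 | 4.008 | 3.955 (−1.3%) | 4.033 (+0.6%) |
| 0.25 | 4.021 | 4.025 (+0.1%) | 4.091 (+1.7%) |
| 0.1 | 4.011 | 4.083 (+1.8%) | 4.142 (+3.3%) |

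Sparse strata take back most of the gain from crossing. With 20 centers, about 4 to 16 subjects fall in one-arm strata and contribute nothing. IGA alone does better, but these runs assume that center does not matter.

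**5. Replacing center with region.** CMH by IGA × region against CMH by center, with 18 centers and center effects with the SD shown (logit scale):
- SD 0.4: mean z +0.3% to +3.8% when severe success is 0.1-0.3 of moderate; 0% to −0.9% when it is 0.5-0.75.
- SD 0.8: −4% to +2%.
- SD 1.2: −1% to −8%; at 18% vs 9%, power falls by about 3 to 7 points.

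Dropping center can cost more than IGA returns.

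**6. Keeping center and adding IGA as a main effect.** Assumptions: 18 centers, 2:1 blocks within center, center SD 0.4 or 0.8, severe share 10-35%, odds ratio 0.5 to 0.1; 1,500 trials per scenario, 2,500 under the null. The comparison is with the same logistic model without IGA.
- Mean z never fell. The gain was 0-0.5% when IGA was weakly prognostic and severe disease rare, about 2% in the middle case (30%, odds ratio 0.25) and 4-5% in the strongest.
- As equivalent sample size: 1.02² = 1.04 and 1.05² = 1.10, so about 4% and 10% more subjects.
- At 18% vs 9%, power changed by about 0 to +4 points.
- One-sided type I error was 1.9-2.8%. Simulation error around 2.5% is ±1.96 × √(0.025 × 0.975/2500) = ±0.6 points.

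The choice of comparator matters. The logistic score statistic uses n in each center's variance where CMH uses n − 1. With 348/18 = 19.3 subjects per center, it exceeds the CMH z by √(19.3/18.3) = 1.027 even without IGA. Comparing directly with CMH would credit IGA with a further 2.7% that it did not earn.

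**The case against.** The strongest reply is that this is preference, not error. The plan prespecifies a valid stratified test with a defined pooling rule. Randomization means that leaving out a predictor neither biases the test nor raises its type I error, and at the planned rates nothing visible changes. All of that stands.

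It is also true that the gain rests on inputs the documents do not give: the severe share and success by baseline IGA. The 18% vs 9% scenario is likewise a what-if. If IGA is only weakly prognostic, the gain is near zero.

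A reader might infer stronger things that the documents do not support:
- **That the primary result would be biased or underpowered.** It would not; power is about 99% either way.
- **That the change is free.** It alters protocol text and the combination of imputed results.
- **That IGA should be crossed with center, or region put in its place.** Steps 4 and 5 show that both can lose precision, and center is the factor on which the pooling and consistency checks of Section 12.5.4 rest.
- **That the EASI endpoints need the same change.** EASI 75 is a percentage fall from the subject's own baseline, so the two-versus-three-grade argument does not carry over, and no calculation supports it.
- **That the plan ignores baseline IGA throughout.** It is used in imputation and as a descriptive subgroup.

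What remains is that the form keeping center and adding IGA as a main effect did not lower mean z in any scenario tried.

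**Conclusion.** The point holds as an optional improvement. The primary test omits a baseline value that is built into its own endpoint and is already collected. Adding it beside center is worth about 0% to +5% in mean z, and about 0 to +4 power points if the rates are 18% vs 9%, without material type I error inflation. At the planned rates the benefit is negligible. Protection against imbalance is real but small: about 0.6 percentage points on the treatment difference for a one-SD imbalance in the middle case.

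These sizes depend on the assumed severe shares (10-35%), odds ratios (0.5 to 0.1) and center SDs (0.4 and 0.8). The direction rests only on IGA being prognostic, which the success definition makes likely but the documents do not show.

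**What to change.** For IGA success at Week 6 and for the IGA-success secondaries at Weeks 4, 10 and 2, specify a logistic model with treatment, analysis center and baseline IGA (3 vs 4) as main effects. Prefer a score or likelihood-ratio test, because the Wald test gives up some of the gain. Keep the center-stratified CMH as a sensitivity analysis. If the sponsor would rather leave the primary test alone, prespecify this model as supportive.

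Costs:
- **Documents.** The Synopsis and Sections 12.5.1 and 12.5.2 name the CMH, so a documented protocol change is needed before unblinding, not SAP wording alone.
- **Imputation.** Section 12.8.3 normalizes CMH statistics before combining them, and that step must be rewritten. An adjusted log odds ratio pools directly in PROC MIANALYZE, but that is a Wald inference. A score or likelihood-ratio statistic needs its own stated combination rule.
- **Sparse centers.** The design rates imply 232 × 0.236 + 116 × 0.063 ≈ 62 successes, or about 3 per center with 20 centers. State in advance what happens at a center with none. Fitting the model conditionally on center would handle this, and would also remove the n versus n − 1 difference in step 6.
- **Reporting.** The adjusted odds ratio is conditional on baseline IGA, so report the arm percentages and their difference beside it.
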